Dietary intervention: Using methods we have established for an ongoing randomized clinical trial with 8 weeks of lentil supplementation, we will prepare 7 mid-day meals per participant per week to deliver a dose of 0 or 3 cups of lentils per week for the experimental and control groups. Meals are matched for macronutrient content (except for fiber), and ground turkey replaces lentils in the control meals. Participants will be instructed to consume food provided for their midday meal, and then to proactively reduce portion sizes and to not eat beyond fullness at the evening meal. This strategy exploits the satiety effect of pulses at the midday meal and the 'second meal effect' in which volitional consumption is reduced at the next meal, the evening meal.

A brief 4 pm online survey addressing satiety and a brief 8 PM online survey addressing gastrointestinal issues will be delivered once a week during the 12-week intervention to participants through personalized e-mails or texts. Each participant will be surveyed once weekly to determine whether they consumed the experimental meal that day, their perceptions of hunger, fullness, satiety, and satisfaction with that day's meal (at 4:00 pm), and their gastrointestinal comfort (level of bloating, flatulence, cramping, and comfort) throughout the day (at 8:00 pm). This methodology has been successfully implemented in our ongoing study to demonstrate that lentil meals are equally pleasing, produce greater satiety, and are well-tolerated.

Vist 3 and 4:

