Linear mixed effects models were used to assess the impact of a week and meal interaction on satiety measures. GI symptom severity was analyzed through a linear mixed effects model with symptom type and a week and meal interaction as predictors. Subject was the random effect for models assessing satiety and GI symptom severity.

Descriptive summary statistics were performed for participant physical and biological characteristics with general linear models used to determine if participants on average differed between meal groups before the intervention began. General linear models were used to assess

the impact of the dietary intervention on the following categories of variables: anthropometric measures (weight, fat mass percent, visceral adipose, and waist circumference); fasting blood lipid measures (CHOL, HDL, LDL, TG); fasting glycemic measures (GLU, INS, HOMA-IR); and fasting inflammation markers (GM-CSF, IFN- γ , TNF- α , IL-1 β , IL-6, IL-10, IL-17, IL-23). Fasting inflammation markers were normalized using r package bestNormalize [38] prior to statistical analysis. Dependent variables were calculated as the change in values from baseline (post-intervention – pre-intervention). Predictor variables were shared within each category of variables and are as follows: anthropometric measures –meal group; blood lipid measures –meal group, visceral adipose tissue; glycemic measures –meal group, visceral adipose tissue, change in BMI, HbA1c; inflammation measures –meal group, visceral adipose tissue. Predictor variables for glycemic measures were chosen based on previous findings by Zeevi and colleagues [39].

Analysis of postprandial metabolic (TG, GLU, INS) and inflammatory (GM-CSF, IFN- γ , TNF- α , IL-1 β , IL-6, IL-10, IL-17, and IL-23) measures were conducted by summarizing each makers measurements at timepoints 0 (fasting) and 1, 2, 3, 4, and 5 hours postprandially as net area under the curve (AUC) using the auctime [40] R package. Each dependent variable was then summarized as the change in AUC (post-intervention – pre-intervention). AUC values for inflammation markers were normalized using r package bestNormalize [38] prior to statistical analysis. General linear models were used to assess the impact of intervention meal group on each dependent variable. Predictor variables were identical to variables utilized in corresponding fasting models.

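### All five glycemic models adjust for change in BMI, a post-randomisation variable that the pulse meals may themselves alter, so they do not estimate the total effect of the randomised diet.

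*Combined protocol and SAP*

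**What the plan says.** The Statistical Plan states that general linear models assess "the impact of the dietary intervention on the following categories of variables", with post-minus-pre change as the dependent variable. For fasting glucose, insulin and HOMA-IR the predictors are "meal group, visceral adipose tissue, change in BMI, HbA1c". The reason given is the findings of a cited earlier study. For the postprandial AUCs the aim is put in similar terms: "General linear models were used to assess the impact of intervention meal group on each dependent variable". The covariates follow by rule: "Predictor variables were identical to variables utilized in corresponding fasting models". The lipid and inflammation models use meal group and visceral adipose tissue only. Weight is among the anthropometric outcomes, which are modelled on meal group alone.

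Under Study Protocol, Dietary intervention, the rationale is: "This strategy exploits the satiety effect of pulses at the midday meal". It continues with a second-meal effect "in which volitional consumption is reduced at the next meal, the evening meal". The same section reports from the group's ongoing study that "lentil meals are equally pleasing, produce greater satiety, and are well-tolerated". Randomisation takes place after Visit 2, before the 12-week diet begins.

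**The concern.** A change in BMI over the trial needs a measurement taken after randomisation. The protocol supplies a causal route to it from the assigned meals: pulses increase satiety, satiety lowers later intake, and lower intake can lower weight. The plan itself treats weight as a possible result of the diet, because it tests weight by meal group. Holding BMI change constant in the glycemic models then asks a different question: how the arms would differ in glycemia at equal BMI change. No objective asks for a weight-independent effect, no mediation aim is stated, and no glycemic model without this covariate is described.

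Two things can go wrong. The part of the effect that runs through BMI is removed. In addition, conditioning on a consequence of treatment opens a path through any unmeasured common cause of BMI change and glycemic change (physical activity or overall diet quality, for instance), so what remains need not equal the direct effect either. That a variable predicts glycemia does not make it a valid adjustment in a randomised comparison if treatment can alter it.

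At stake is the trial's evidence on glucose and insulin, which bears on the overall goal concerning type 2 diabetes risk profiles. A benefit working partly through weight could be understated or missed.

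**Working it through.** **Number of models.** Fasting: glucose, insulin, HOMA-IR = 3. Postprandial AUC: glucose, insulin = 2. Total 3 + 2 = 5. Postprandial triglyceride follows the lipid predictor set, so it does not contain change in BMI.

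**Inputs.** The documents give no arm difference in BMI change, no slope of glycemic change on BMI change, no SD and no sample size. There is therefore no figure in the plan to reproduce, and every value below is an assumption in residual SD units.

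**Model.** G is meal group (1:1), M is change in BMI, Y is change in the glycemic outcome, and U is an unmeasured common cause. U, e1 and e2 are standard normal.

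- M = aG + gU + √(1 − g²)·e1, so Var(M | G) = 1
- Y = cG + bM + hU + e2

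Here a is the arm difference in BMI change, b the slope on BMI change, c the direct effect of the meals, and g and h the effects of U on M and Y. Then:

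- total effect (M left out) = c + ab
- meal coefficient with M in the model = c − agh
- gap = (c + ab) − (c − agh) = a(b + gh)

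**Gap with b = 0.3 and no common cause (gh = 0).**

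| a | 0 | −0.1 | −0.2 | −0.3 | −0.5 | −0.8 |
|---|---|---|---|---|---|---|
| absolute gap, 0.3 × \|a\| | 0 | 0.03 | 0.06 | 0.09 | 0.15 | 0.24 |

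**Adding a common cause, with a = −0.5, b = 0.3, c = 0.** The total effect is −0.5 × 0.3 = −0.15. The adjusted coefficient is 0.5 × gh:

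| g = h | gh | adjusted (formula) | adjusted (simulated, n = 2,000,000) |
|---|---|---|---|
| 0 | 0 | 0 | −0.001 |
| 0.3 | 0.09 | +0.045 | +0.043 |
| 0.45 | 0.2025 | +0.101 | +0.099 |
| 0.6 | 0.36 | +0.180 | +0.178 |

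If U acts in opposite directions (gh = −0.09), the adjusted value is −0.045.

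**With a direct benefit, c = −0.20** (separate simulation, n = 400,000 per scenario; b = 0.3 to 0.5).

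| a | total effect | adjusted, no common cause | adjusted, g = h = 0.5 |
|---|---|---|---|
| 0 | −0.20 | about −0.20 | about −0.20 |
| −0.25 | −0.275 to −0.325 | about −0.20 | about −0.14 |
| −0.5 | −0.35 to −0.45 | about −0.20 | about −0.07 |

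The model without M recovered the total effect in every row, to within about 0.01.

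**Precision.** With no common cause, SE(adjusted)/SE(unadjusted) = √[(1 + a²/4)/(1 + b²)]. At b = 0.3:

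- a = 0: √(1/1.09) = 0.958, an SE 4.2% lower with adjustment
- a = −0.5: √(1.0625/1.09) = 0.987, 1.3% lower
- a = −0.8: √(1.16/1.09) = 1.032, 3.2% higher
- break-even at |a| = 2b = 0.6

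With g = h = 0.6 and a = 0, the residual variances are 1 + 0.36 × 0.64 = 1.2304 adjusted and 1 + 0.09 + 0.36 + 2 × 0.3 × 0.36 = 1.666 unadjusted. The ratio is √(1.2304/1.666) = 0.859, so adjustment lowers the SE by 14%.

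**The case against.** The strongest reply is that the arms may hardly differ in BMI change. Meals are matched for macronutrients apart from fiber, and the advice to eat less in the evening goes to participants without distinction by arm. Much of any weight change could then be common to both arms, and adjusting for it would mainly reduce noise. This stands as a reason to expect that the distortion may be small, and at a = 0 it is zero. It does not rescue the plan. The protocol attributes the satiety effect to pulses specifically, and a main model should not be valid only if one of the trial's own outcomes shows no effect.

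Other limits also stand:

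- Glycemic measures are in no numbered objective. Objective 1 concerns postprandial triglyceride and inflammation, whose models do not contain change in BMI.
- All sizes are assumed. A reversed sign needs particular conditions: at a = −0.5 with g = h = 0.3, 0.45 or 0.6, the beneficial direct effect must be smaller than 0.045, 0.10 or 0.18. With a direct effect of −0.20, no scenario above changed sign.
- Adjustment removes only what is associated with BMI change. Effects of lower intake that bypass BMI stay in the coefficient.
- The weight, satiety and dietary-intake models would show readers whether the route operated. They would not supply a total-effect estimate for glycemia.

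**Conclusion.** The concern holds. The five glycemic models are presented as measuring the impact of the diet but adjust for a post-randomisation variable that lies on the protocol's own causal route, and no model without it is described. That mismatch is plain from the text and depends on no assumed number.

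Its numerical consequence cannot be determined from the documents. It is zero if mean BMI change is equal between arms, and otherwise a(b + gh). Across the assumed values above with lower BMI in the pulse arm and a zero or same-direction common cause, the gap runs from 0.03 to 0.375 SD, and adjustment hides benefit. These values rest on a linear model with one common cause and are illustrations, not predictions.

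The point should be fixed, but it is confined to the glycemic outcomes. The triglyceride and inflammation models escape it as far as change in BMI is concerned. They stay clear only if visceral adipose tissue is a baseline value, and the plan gives no time point for it.

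**What to change.** Make the main fasting and postprandial glycemic models meal group plus pre-randomisation covariates only: visceral adipose tissue and HbA1c, each stated to be a baseline value. The baseline value of the outcome or baseline BMI may be added but is not needed to cure this defect. Stating the time point of visceral adipose tissue also settles the question for the lipid and inflammation models.

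If a weight-independent effect is of interest, keep the model with change in BMI as a labelled exploratory mediation analysis and state that it assumes no unmeasured common cause of BMI change and glycemia.

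The plan is written in the past tense. If the analyses have been run, report the model without change in BMI as the total-effect estimate, show the existing model beside it, and disclose the change.

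The cost is revised SAP wording and a re-run of five models, with no new data. If the arms do not differ in BMI change, some precision is given up: adjustment would have lowered the SE by about 4% at b = 0.3 with no common cause, and by more (14% in the g = h = 0.6 example) if BMI change and glycemic change are strongly correlated.
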